### 2.1.7 Rationale

Based on the dosing regimens that have been tolerated in these ongoing trials we propose a starting dose for single agent therapy of 45mg/m^2/day daily x5 on a 28 day cycle. The majority of patients enrolled on our trial will not have had extensive therapy with cytotoxic agents and hence would not be expected to experience the degree of bone marrow toxicity that was observed in patients on these earlier trials. Because GIST, RCC, and PHEO/PGL are more indolent tumors it may be expected that a more prolonged course of treatment will be given to our patients. In order to facilitate more long-term dosing of the drug two dose de-escalations of approximately 30% will be allowed.

## 3 PATIENT SELECTION

### 3.1 ELIGIBILITY CRITERIA

#### 3.1.1 Inclusion Criteria:

Patients must:

##### 3.1.1.1 Have recurrent or refractory/unresectable disease for which there is no known curative therapy.

- Wild type-GIST: Patients with recurrent or progressive disease will be eligible. Newly diagnosed patients with resectable localized disease will not be eligible. Newly diagnosed patients with metastatic disease and newly diagnosed patients with residual tumor following surgical debulking will be eligible.

- PHEO/PGL: Patients with recurrent or progressive disease will be eligible. Newly diagnosed patients with PHEO/PGL that is metastatic at diagnosis and/or unresectable will be eligible. Patients with PHEO/PGL with localized (non-metastatic), resectable disease will not be eligible.
- Renal cell cancer associated with HLRCC: Patients with localized, resectable HLRCC-associated renal cell cancer will not be eligible. Patients with metastatic and/or unresectable HLRCC-associated renal cell cancer will be eligible.

3.1.1.2 Have one of the following confirmed histologically, cytologically, or through biochemical testing:

- wild-type GIST (GIST without KIT or PDGFRA mutation);
- PHEO/PGL with a germline mutation in SDHA, SDHB, SDHC, or SDHD;
- renal cell cancer associated with HLRCC.

Testing will be performed in CLIA certified labs using genetic tests for KIT/PDGFR $\alpha$  and testing panels developed for patients with PHEO/PGL. Results from outside labs will be accepted. Pathologic diagnosis will be reviewed and verified at the Clinical Center.

3.1.1.3 Age: be  $\geq$  12 years of age

Because there is no dosing or adverse event data currently available on the use of SGI-110 in children  $<$  18 year of age, children  $<$  12 years of age will be excluded from this study, but may be eligible for future pediatric trials should the results of the study be positive.

3.1.1.4 Measurable disease:

Have measurable disease, defined as at least one lesion that can be accurately measured in at least one dimension (longest diameter to be recorded for non-nodal lesions and short axis for nodal lesions) as  $\geq$  20 mm with conventional techniques or as  $\geq$  10 mm with spiral CT scan. See Section 8.2.2 for the evaluation of measurable disease (RECIST v1.1).

3.1.1.5 Prior Therapy

3.1.1.5.1 Prior therapy requirements:

- Wt-GIST: Because there are no standard chemotherapy regimens known to be effective for wt-GIST, previously untreated participants are eligible.
- PHEO/PGL with germline SDH subunit mutation:  $^{131}\text{I}$ -MIBG in patients with MIBG avid tumors or cytotoxic chemotherapy (CVD or temozolomide) is required prior to enrollment on this trial. However, patients who have refused cytotoxic chemotherapy or for whom treatment on this protocol prior to receiving cytotoxic chemotherapy is felt to be in the best interest for the patient by the local investigator will also be eligible.
- HLRCC-associated renal cell cancer: Because there are no standard chemotherapy regimens known to be effective for HLRCC-associated renal cell cancer, previously untreated participants are eligible.

3.1.1.5.2 Prior therapy wash-out period requirements

- Participants must be at least 4 weeks from prior surgical procedures and surgical incisions must be healed.

- Participants must have had their last fraction of external beam radiation therapy at least 4 weeks prior to enrollment. Participants with prior radiation therapy must be at least 4 weeks post therapy *and* have had progression of disease outside the radiation port.
- Participants must have had their last dose of cytotoxic chemotherapy at least 28 days prior to enrollment, their last dose of biological therapy, such as biological response modifiers (e.g., cytokines), immunomodulatory agents, vaccines, differentiating agents, used to treat their cancer at least 28 days prior to enrollment, their last dose of a monoclonal antibody at least 28 days prior to enrollment, and their last dose of any investigational agent at least 28 days prior to enrollment.
- Participants must have recovered from the acute toxic effects of prior therapy to a grade 1 (CTCAE v.5.0) level prior to enrollment (does not apply to alopecia).

3.1.1.6 Performance Level: ECOG performance status  $\leq 2$  or Karnofsky  $\geq 60\%$  in patients  $> 16$  years of age, Lansky  $\geq 60$  for patients  $\leq 16$  years of age (See Appendix I).

3.1.1.7 Have normal organ and marrow function as defined below:

- absolute neutrophil count	$\geq 1,500/\text{mcL}$
- platelets	$\geq 100,000/\text{mcL}$
- total bilirubin	within normal institutional limits
- AST(SGOT)/ALT(SGPT) normal	$\leq 2.5 \times$ institutional upper limit of
- creatinine	within normal institutional limits
OR	
- creatinine clearance	$\geq 60 \text{ mL/min}/1.73 \text{ m}^2$ for patients with creatinine levels above institutional normal.

3.1.1.8 Birth Control:

The effects of SGI-110 on the developing human fetus are unknown. For this reason and because decitabine is known to be teratogenic, women of child-bearing potential and men must agree to use adequate contraception (hormonal or barrier method of birth control; abstinence) prior to study entry and for the duration of study participation, and for 6 months following participation. Should a woman become pregnant or suspect she is pregnant while she or her partner is participating in this study, she should inform her treating physician immediately.

3.1.1.9 Ability of subject or legal guardians (if the patient is  $< 18$  years old) to understand and the willingness to sign a written informed consent document.

3.1.2 Exclusion Criteria

Patients with any one the following will be excluded:

- 3.1.2.1 Ongoing radiation therapy, chemotherapy, hormonal therapy directed at the tumor, immunotherapy, or biologic therapy, including investigational agents for their disease.
- 3.1.2.2 History of allergic reactions to SGI-110 or decitabine.
- 3.1.2.3 Uncontrolled intercurrent illness including, but not limited to, symptomatic congestive heart failure, unstable angina pectoris, cardiac arrhythmia, symptomatic

pulmonary disease or psychiatric illness/social situations that would limit compliance with study requirements.

#### 3.1.2.4 Pregnant or breastfeeding

Pregnant women are excluded from this study because SGI-110 is a derivative of decitabine which has the potential for teratogenic or abortifacient effects. Because there is an unknown but potential risk for adverse events in nursing infants secondary to treatment of the mother with SGI-110, breastfeeding should be discontinued if the mother is treated with SGI-110. These potential risks may also apply to other agents used in this study.

- 3.1.2.5 Any evidence of severe or uncontrolled systemic disease, active infection, active bleeding diatheses, or renal transplant, including any patient known to have hepatitis B, hepatitis C, or human immunodeficiency virus (HIV) will be excluded. Patients with HIV who have adequate CD4 count, not requiring antiretroviral medication, may be enrolled.
- 3.1.2.6 Patients who, in the opinion of the investigator, may not be able to comply with the safety monitoring requirements of the study.

### 4 RECRUITMENT AND REGISTRATION

#### 4.1 RECRUITMENT

In addition to posting this study on clinicaltrials.gov and the NCI website, patients who may be eligible will be invited to undergo screening during their participation in CCR Clinical studies, i.e. GIST Clinic held by POB, and RCC Clinic held by UOB, and PHEO/PGL Clinic held by NICHD.

#### 4.2 SCREENING EVALUATION

Eligibility will be determined during a pre-study evaluation period after subjects have signed a consent (either a screening consent or this treatment consent). Subject information must be entered onto a screening log and for subjects not registered (enrolled) on the treatment portion of the study, a brief reason will be entered onto the screening log.

Screening blood tests should be performed within 72 hours and imaging studies within 4 weeks prior to enrollment on the trial unless otherwise stated. Any abnormal laboratory result that might preclude eligibility can be repeated within 24 hours.

##### 4.2.1 History and physical examination

- Complete history, including prior and concurrent therapy; physical examination including documentation of measurable disease, performance status, blood pressure, height, weight, signs and symptoms.

##### 4.2.2 Imaging evaluation

- Assessment of measurable disease sites by appropriate radiological evaluation. This may include a CT scan of chest, abdomen and pelvis and primary tumor, MRI scan of primary tumor and FDG-PET scan, as clinically indicated.

##### 4.2.3 Hematology

- Complete blood count with differential and platelets.

#### 4.2.4 Chemistries

- Electrolytes (including sodium, potassium, chloride, CO2), calcium, phosphorus, magnesium, creatinine, BUN, glucose, ALT, bilirubin, urinalysis, total protein, albumin, CPK, and chromogranin A. Evaluation of catecholamine production by tumor (serum normetanephrine and metanephrine, urine if possible) will be performed in patients with PHEO/PGL only.

#### 4.2.5 Urine or serum pregnancy test for all females of childbearing potential.

#### 4.2.6 Pathologic/Tissue Evaluation

- Pathologic diagnosis will be reviewed and verified at the Clinical Center. Expression of SDH complex subunits and/or FH will be evaluated by immunohistochemistry in available pre-treatment tumor samples in the Clinical Center Laboratory of Pathology. GIST without Kit or PDGFRA mutation will be determined using standard approved tests.

#### 4.2.7 For patients with PHEO/PGL

- Germline SDH subunit mutations will be determined using standard approved testing. Approved testing done outside of the Clinical Center will be accepted for these patients.

### 4.3 REGISTRATION PROCEDURES

#### 4.3.1 IWRS

Patient Enrollment will be facilitated using the Interactive Web Response System (IWRS). IWRS is a web-based registration system available to users on a 24/7 basis. On a successful registration, IWRS will assign a patient number and assign the treatment. Patient enrollment data entered by Registrars in IWRS will automatically transfer to the NCI's clinical data management system, Medidata Rave. IWRS will provide a printable confirmation of registration and treatment information. Please retain a copy of this confirmation for your records.

- Users must have a valid CTEP-IAM account (*i.e.*, CTEP username and password) to access the IWRS system.
- Users defined with the Registrar role will have the ability to register patient in the study.
- Users defined with the Client Administrator role will have the ability to manage accrual limits, open and close treatment assignments as well as approve slot reservations, if applicable to the study.

#### 4.3.2 OPEN / IWRS

Patient enrollment will be facilitated using the Oncology Patient Enrollment Network (OPEN). OPEN is a web-based registration system available to users on a 24/7 basis. It is integrated with the CTSU Enterprise System for regulatory and roster data interchange and with the Theradex Interactive Web Response System (IWRS) for retrieval of patient registration/randomization assignment. Patient enrollment data entered by Registrars in

OPEN / IWRS will automatically transfer to the NCI's clinical data management system, Medidata Rave.

The OPEN system will provide the site with a printable confirmation of registration and treatment information. Please retain a copy of this confirmation for your records.

#### 4.3.3 OPEN/IWRS User Requirements

OPEN/IWRS users must meet the following requirements:

- Have a valid CTEP-IAM account (*i.e.*, CTEP username and password).
- To enroll patients: Be on an ETCTN Corresponding or Participating Organization roster with the role of Registrar.
- Have regulatory approval for the conduct of the study at their site.

Prior to accessing OPEN/IWRS, site staff should verify the following:

- All eligibility criteria have been met within the protocol stated timeframes.
- If applicable, all patients have signed an appropriate consent form and HIPAA authorization form.

### 4.4 LOCAL REGISTRATION FOR NCI CCR

Authorized staff must register an eligible candidate with NCI Central Registration Office (CRO) within 24 hours of signing consent. A registration Eligibility Checklist from the website (<http://home.ccr.cancer.gov/intra/eligibility/welcome.htm>) must be completed and sent via encrypted email to: NCI Central Registration Office [[contact]](mailto:[contact]). After confirmation of eligibility at Central Registration Office, CRO staff will call pharmacy to advise them of the acceptance of the patient on the protocol prior to the release of any investigational agent. Verification of Registration will be forwarded electronically via e-mail to the research team. A recorder is available during non-working hours.

## 5 STUDY IMPLEMENTATION

### 5.1 STUDY DESIGN

This is a single site, open label, phase II study design using a small optimal two-stage design to evaluate the clinical response in three groups of patients:

1. wild-type GIST (GIST without Kit or PDGFRA mutation)
2. PHEO/PGL in patients with germline SDH subunit mutation (SDH deficient PHEO/PGL), or
3. RCC associated with HLRCC

Adults and children (greater than or equal to 12 years of age) with measurable localized or metastatic or unresectable wild-type GIST, SDH deficient PHEO/PGL, or HLRCC-associated

RCC will be eligible for trial participation. SGI-110 will be administered subcutaneously at 45mg/m^2/day x 5days on a 28-day cycle. Cycles may be repeated until there is evidence of tumor progression clinically or by RECISTv1.1 or there is intolerable toxicity that is not alleviated by dose reduction.

SGI-110 activity will be assessed by radiographic response of measurable disease using RECISTv1.1. Patients will be carefully monitored for toxicity and response. Time to progression, overall survival and quality of life will be evaluated as secondary objectives.

## 5.2 DRUG ADMINISTRATION

SGI-110 will be administered subcutaneously, preferably in the abdominal area at 45mg/m^2/day x 5 days on a 28-day cycle. SGI-110 is available in a two-vial system, (1) SGI-110 for Injection 100 mg, and (2) SGI-110 Diluent for Reconstitution 3 mL.

SGI-110 drug product admixed with the custom diluent as described in section 15.1. The reconstituted SGI-110 solution is stable for 1 week under refrigerated conditions.

SGI-110 should be injected slowly (up to one minute) as some injection site discomfort or pain may be experienced. Care must be taken to avoid intradermal injection as this may result in injection site pain. To prevent injection site pain, patient should be directed to apply ice packs to the injection site before and after the injection. If the injection pain continues despite these measures, pre-treatment with topical or systemic analgesics may be considered. Patients will be observed in clinic for at least one hour after the first dose of SGI-110. Vital signs including blood pressure, heart rate, and respiratory rate will be obtained and injection site will be monitored for signs of local reaction every 20-30 minutes in clinic for 1-hour post injection after the initial dose of SGI-110.

## 5.3 DOSE MODIFICATIONS

Although not a phase 1 study, toxicity will be evaluated and treatment limited by the toxicities defined below. This study will utilize the CTEP Common Terminology Criteria for Adverse Events (CTCAE) Version 5.0 for toxicity and Adverse Event grading and reporting. An adverse event must be judged to be possibly, probably, or definitely related to SGI-110 to be a treatment limiting toxicity. Because it is possible that longer-term administration of the drug may be required in these patient populations, two dose reductions of approximately 30% will be allowed for patients who develop toxicity determined to be treatment related.

If a subject misses or skips a dose the dose will be given the next day. When a missed or skipped dose occurs, the research team should be notified to provide guidelines to the subject on whether to proceed with further doses.

SGI-110 will be held for treatment-limiting toxicities and re-started at the reduced dose after resolution of toxicity to a grade 1 or baseline.

Treatment-limiting toxicity is defined as:

- Toxicities that are possibly, probably or definitely related to SGI-110 and are  $\geq$  grade 3, **unless** the toxicity resolves/reversible within 72 hours with supportive care.
- In addition, persistent grade 2 toxicities will be considered dose-limiting if they are intolerable to the patient.

If the patient experiences a treatment limiting toxicity after two dose reductions, SGI-110 will be discontinued permanently.

Dose Level	Dose reduction (mg/m  /dose)	Dose reduction (%)
Dose -1	30mg/m  /dose	~30%
Dose -2	20mg/m  /dose	~30%

## 5.4 QUESTIONNAIRES (APPENDIX III AND APPENDIX IV)

The pediatric PROMIS instruments and the Distress Rating Tool will be administered to all consenting patients who speak English or Spanish with parallel Parent Proxy instruments administered to parents of patients ages 12-17. These instruments will be administered at baseline, at the end of cycle 4 and every 4 cycles thereafter, and at the time a patient is taken off treatment (see Section 5.7). Since the measures have not been validated in other languages, participation in this portion of the study will be limited to subjects who speak either English or Spanish.

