Patient-Reported Outcomes Measurement Information System (PROMIS) is a health related quality of life measurement tool that was developed by NIH to standardize patient-reported outcomes for national use by research clinicians. Two versions of PROMIS are available to researchers: computer-adaptive tests (CATs) and short forms. The short forms are brief, static instruments that have demonstrated similar reliability to the longer, dynamic CATs, which provide precise measures for studying populations with widely varied responses and longitudinal self-report data . Each short form includes 4 to 8 items, measures reported health outcomes in the past 7 days on a Likert type scale, and takes approximately 5 minutes

to complete. PROMIS instruments, measuring a broad range of health domains, have been validated for adults ( $\geq 18$ ) with a variety of health conditions .

Early evaluation of PROMIS pediatric instruments indicates validity for children ages 8 to 17 , hence this is appropriate for the age group 12-17 years old in this trial. Six pediatric PROMIS instruments and six parallel Parent Proxy PROMIS instruments (See Appendix III) are available to assess five quality of life health domains (physical function, pain interference, fatigue, emotional health, and social health) and are intended for use with both healthy and chronically ill pediatric populations. This protocol will utilize pediatric PROMIS short forms and the Parent Proxy short forms to assess symptoms that can be associated with GIST. These include physical function, anxiety, depressive symptoms, fatigue, pain interference, and peer relationships.

Assessments of Health-Related Quality of Life will be administered at the start of therapy, at the end of cycle 4 and then every 4 cycles thereafter, and then at the end of therapy. The PROMIS Patient Outcome Measures (6) and patient-reported symptom severity (Distress and Symptom Checklist) will provide us with essential information regarding how symptoms may change over the course of treatment, and will also provide a more in-depth assessment of the known toxicities associated with SGI-110 in this patient population.

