The PI of the study will be notified of participants who have scores 2 standard deviations above the mean normative t-score of 50 (so a t-score of 70) on the PROMIS depression short form (suggesting high depression), and these participants will be assessed for suicidal ideation by a member of the psychosocial team. Those found to have suicidal ideation will be referred to the NIH psychiatry service.

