### 5.4.1 PROMIS

The Patient–Reported Outcome Measurement Information System (PROMIS®), funded by the National Institutes of Health to provides clinicians and researchers access to efficient, precise, valid, and responsive parent– and child–reported measures of health and well–being.

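### Section 5.4 gives the pediatric PROMIS forms to every patient, although Section 2.1.6.1 supports them only to age 17 and no body text assigns the printed adult forms to anyone

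*Combined protocol and SAP*

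**What the plan says.** Section 5.4 sets the rule for who completes what: "The pediatric PROMIS instruments and the Distress Rating Tool will be administered to all consenting patients who speak English or Spanish". The same sentence then adds a second component for minors, "with parallel Parent Proxy instruments administered to parents of patients ages 12-17". The age range in that second part limits the proxy forms only. The pediatric forms carry no upper age limit.

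Section 2.1.6.1 gives the supporting evidence. On the pediatric forms it says "Early evaluation of PROMIS pediatric instruments indicates validity for children ages 8 to 17" and concludes "hence this is appropriate for the age group 12-17 years old in this trial". On what will be used it says "This protocol will utilize pediatric PROMIS short forms and the Parent Proxy short forms to assess symptoms that can be associated with GIST". It also says that "PROMIS instruments, measuring a broad range of health domains, have been validated for adults", but this is a general statement about PROMIS and assigns no form to trial patients. Later in the same section the six PROMIS measures are mentioned without saying which age version is meant.

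Section 5.4.1 describes PROMIS as providing "responsive parent– and child–reported measures of health and well–being" and does not mention adult self-report. The quality-of-life row of the study calendar (Section 5.6) names PROMIS without a version.

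Appendix III, cited in the heading of Section 5.4, contains pediatric sets in English (16.3.1) and Spanish (16.3.2), a parent-proxy set in English (16.3.3), and adult sets in English (16.3.4) and Spanish (16.3.5). Section 5.1 confirms that adults are eligible.

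**The concern.** The rule in Section 5.4 applies the pediatric instruments outside the age range the protocol gives for them. Staff face two conflicting courses with an adult patient. If they follow Section 5.4, they use a form the protocol supports only for minors. If they use the adult forms in the appendix, they depart from Section 5.4 as written. Different staff could resolve this differently, leaving a mixture of versions among adults.

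Pain and quality of life are a named secondary objective (Section 1.1.2), and Section 12 plans to relate changes in quality of life to response. Adult results from child-oriented forms, or from an unplanned mixture of versions, would be hard to interpret.

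There is one further consequence, conditional on Section 5.4 being followed literally. Section 2.1.6.1 uses a PROMIS depression T-score of 70 to trigger notification of the principal investigator, after which "these participants will be assessed for suicidal ideation by a member of the psychosocial team". In adults that score would then come from the pediatric form. Nothing in the documents shows the direction or size of any resulting error in the T-score, and none is claimed here.

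**Working it through.** There is no design figure to reproduce. The check is a comparison of every place where PROMIS forms are described or assigned, followed by a count of items.

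**Step 1. Assignment of each form set**

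| Form set | Printed in Appendix III | Assigned in the body text to | Age support in Section 2.1.6.1 |
|---|---|---|---|
| Pediatric | 16.3.1 (English), 16.3.2 (Spanish) | All consenting English- or Spanish-speaking patients (5.4) | 8-17; suitable for 12-17 in this trial |
| Parent proxy | 16.3.3 (English) | Parents of patients aged 12-17 (5.4) | Presented as parallel to the pediatric forms |
| Adult | 16.3.4 (English), 16.3.5 (Spanish) | No one | General statement that PROMIS is validated in adults |

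The first row contains the contradiction and the third row the gap. Printed adult forms without an assignment: 6 + 6 = 12.

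**Step 2. Is it one loose word?** Sections 5.4, 5.4.1 and the sentence in 2.1.6.1 naming the forms to be used all leave out the adult sets. The domains listed in 2.1.6.1 include peer relationships, which is in the pediatric set. The adult set has a Global Health form and no peer form, so that list describes the pediatric set. By contrast, the Distress Thermometer is discussed for both adults and children in 2.1.6.1 and has its own age rule in 5.4.2.

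**Step 3. What an adult would be asked under Section 5.4.** Items per pediatric form in English (16.3.1), and items that explicitly mention other kids or schoolwork:

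| Form | Items | Mention kids or schoolwork |
|---|---|---|
| Mobility | 8 | 2 |
| Anxiety | 8 | 0 |
| Depressive symptoms | 8 | 0 |
| Fatigue | 10 | 1 |
| Pain interference | 8 | 1 |
| Peer relationships | 8 | 4 |
| Total | 50 | 8 |

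8 / 50 = 16%. The Spanish set (16.3.2) gives the same result: 8 + 10 + 8 + 8 + 8 + 8 = 50 items, of which mobility 2, fatigue 1, pain 1 and peer relationships 4 make 8, again 16%. This is a count of wording that plainly does not fit adults. It does not measure bias or loss of validity.

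**Step 4. How many patients.** The documents give no expected split by age. The number aged 18 or over could be anywhere from 0 to the accrual ceiling of 70 (Section 12).

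**The case against.** The best defence is that the intention is easy to see. The heading of Section 5.4 points to Appendix III, where the forms are separated by respondent and two sets are labelled for adult patients. Section 2.1.6.1 notes adult validation and ties the pediatric forms to ages 12-17. The sentence naming the pediatric and proxy forms closes a paragraph about children, so it need not be an exhaustive list. The depression trigger does not name the pediatric form, and none of the eight pediatric depressive-symptom items mentions kids or schoolwork. Quality of life is descriptive and hypothesis-generating (Section 12).

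Much of this stands. A drafting slip is the likely explanation, the depression point is conditional, and no effect on any reported result has been shown. It does not remove the problem. A heading that cites a whole appendix does not tell staff which patient completes which form, and a general validation statement does not either. The one sentence that does assign the pediatric forms gives them to everyone. Clear intent is a reason to correct that sentence.

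Two practical points raised on this side also stand and belong in the correction. Adding the adult forms makes the domain list in 2.1.6.1 incomplete, and the proxy set is printed in English only although Section 5.4 also includes Spanish speakers.

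**Conclusion.** The inconsistency is real: Section 5.4 contradicts the age support in Section 2.1.6.1, and 12 printed adult forms are assigned to no one in the body text. If Section 5.4 is followed literally, every adult patient completes six pediatric forms with 50 items, 8 of them (16%) about other kids or schoolwork, including 1 of 8 pain-interference items and 4 of 8 peer-relationship items. The number of adults affected is an unknown between 0 and 70.

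The effect is confined to the secondary quality-of-life and pain data and to the source of the depression score in Section 2.1.6.1. The response endpoint and the rule of 7 and then 21 evaluable patients per stratum do not depend on it. It should be corrected, because the text states a wrong rule and does not merely omit a detail.

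**What to change.** Replace the assignment sentence in Section 5.4 with one that goes by age, for example:

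> Patients aged 18 or over will complete the adult PROMIS forms (16.3.4 English, 16.3.5 Spanish). Patients aged 12-17 will complete the pediatric PROMIS forms (16.3.1 English, 16.3.2 Spanish), and a parent will complete the Parent Proxy forms (16.3.3). All consenting patients will complete the Distress Rating Tool.

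Then align the related text:

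- In Sections 2.1.6.1 and 5.4.1, add the adult self-report forms to the instruments to be used. In the domain list of 2.1.6.1, show that peer relationships belongs to the pediatric and proxy sets and Global Health to the adult set.
- In the depression paragraph of 2.1.6.1, state that the T-score comes from the participant's own age-appropriate self-report form. The threshold is left as it is.
- State that the proxy set is English only, so that it is clear what happens with Spanish-speaking parents.
- Optionally, say which form is used when a patient turns 18 on study, and that form versions will be summarised separately.

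The cost is wording in Sections 5.4, 5.4.1 and 2.1.6.1. The adult forms are already in Appendix III, so no new instrument or visit is needed. The optional separate summaries would only split the descriptive tables already planned.
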